5.1.2 Efficacy Endpoints Based on Monthly Collection

Migraine Functional Impact Questionnaire (MFIQ)

The MFIQ version 2.0 is a self-administered 26-item instrument measuring the impact of migraine on broader functioning including 4 domains: Impact on Physical Functioning (5 items), Impact on Usual Activities (10 items), Impact on Social Functioning (5 items), and Impact on Emotional Functioning (5 items). In addition, there is 1 stand-alone global item assessing the overall impact on usual activities. Subjects respond to items using a 5-point scale assigned scores from 1 to 5, with 5 representing the greatest burden. Each domain score will be calculated as the sum of the item responses, and the sum will be rescaled to a 0 to 100 scale, with higher scores representing greater burden. The recall period is the past 7 days.

5.1.3 Safety Endpoints

Treatment-emergent Adverse Event (TEAE)

An event categorized as “Adverse Event” on the Events eCRF starting on or after first dose of investigational product, as determined by “Did event start before first dose of investigational product” equal to “No” or missing, and up to the End of Study date.

Serious Treatment-emergent Adverse Event

A treatment-emergent adverse event with the indicator flag “Serious” equal to “Yes” on the Events eCRF.

Treatment-emergent Adverse Device Effect

A treatment-emergent adverse event with the indicator flag “Is there a reasonable possibility that the event may have been caused by the investigational device” equal to “Yes” on the Events eCRF.

5.2 Study Dates

Informed Consent Date

The date on which subject signs the informed consent form.

eDiary Device Assignment Date

The date on which an eDiary device is assigned to a subject for the first time after completion of initial screening.

First Dose Date

First Dose Date is the date on which a subject is administered the first dose of IP following completion of the Baseline period as recorded on the IP Administration eCRF.

Last Dose Date

Last Dose Date is the date on which a subject is administered the last dose of IP during the study, where receiving IP is defined as above.

End of Study (EOS) Date

End of study (EOS) date is defined as the last date on which the subject participates in the study as recorded on the End of Study eCRF.

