8.1.2 Baseline Period

The baseline period can begin after confirmation that all initial eligibility criteria have been met. This can be the same day as the screening visit or within 3 weeks (21 days) of the screening visit. The baseline period will end 1 day before the day 1 visit and must be at least 28 days and no more than 35 days in duration. The compliance in eDiary usage during the baseline period will be assessed on day 1. A subject will either be screen-failed if not demonstrating $\geq 75\%$ compliance in eDiary usage, or enrolled into the open-label treatment period. Subjects who have screen failed may be eligible for rescreening only once, if in the opinion of the investigator, the reason for the initial screen failure has been resolved or is no longer applicable. Once the subject is rescreened, a new screening window will begin. Subjects will retain the same subject identification number assigned at the original screening. If the rescreening period begins more than 45 days after the original signing of the informed consent form, all screening procedures, including informed consent, must be repeated.

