3.1 Study Design

This is a phase 4 open-label study that will enroll subjects with episodic migraine (EM) or chronic migraine (CM) without a predetermined allocation ratio. The study will comprise the following periods:

- A screening period of up to 3 weeks (21 days) for the assessment eligibility criteria. The screening visit may be performed on the same day as the baseline visit
- A baseline period of 4 weeks (28 up to 35 days) to collect data on migraine headaches and acute headache medication use using electronic diary (eDiary) and to assess compliance in eDiary usage **at day 1 visit**
- A 24-week open-label treatment period

Subjects will be screened at the screening visit, and **if eligible, subjects may enter the baseline period at the same visit as screening or may begin baseline procedures up to 3 weeks after the screening visit.** At completion of the baseline period, those who **meet the eligibility criteria and** demonstrate $\geq 75\%$ compliance with eDiary use will be enrolled and will enter the open-label treatment period to receive erenumab either 70 mg or 140 mg subcutaneously (SC) every 4 weeks (Q4W) at the discretion of the investigator.

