5.3 Study Points of Reference

Baseline Assessment

Baseline assessment for the endpoint of the interest is defined as the last non-missing measurement taken or the monthly interval assessed (for endpoints derived from daily eDiary collection) before the first dose of investigational product. In cases where baseline measurements are taken on the same day as IP, it will be assumed that these measurements are taken prior to IP being administered.

Study Day 1

Study Day 1 is defined as the first IP dose date.

Study Day

Study Day is defined as the number of days from Study Day 1.

Before Study Day 1:

$$\text{Study Day} = (\text{Date of Interest} - \text{Date of Study Day 1})$$

On or after Study Day 1:

$$\text{Study Day} = (\text{Date of Interest} - \text{Date of Study Day 1}) + 1$$

Therefore, the study day prior to Study Day 1 is -1.

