5.4 Study Time Intervals

5.4.1 Monthly Intervals for Efficacy Endpoints Derived From Daily Diary Collection

The (4-week) monthly intervals for efficacy endpoints derived from daily eDiary collection will be determined based on each subject's monthly IP dosing dates. When an IP is

missed, discontinued, or no longer required, a 28-day monthly interval will be used. Any eDiary data occurring after EOS date will not be included in the analysis.

Applicable efficacy endpoints utilizing the monthly intervals in **Table 3** include:

- Monthly migraine days (MMD)
- Monthly acute migraine-specific medication days
- Monthly acute headache medication days
- Monthly average migraine pain severity

Table 3. Monthly Intervals for Efficacy Endpoints Derived From Daily Data Collection

Study Period	Assessment Timepoint	Monthly Interval	
		Start Date (Day) ^a	End Date (Day) ^b
Baseline Period	Baseline	Device assignment date	Day prior to study day 1
Open-label Treatment Period	Week 4 (Month 1)	Study Day 1	Week 4 dose date – 1
	Week 8 (Month 2)	Week 4 dose date	Week 8 dose date – 1
	Week 12 (Month 3)	Week 8 dose date	Week 12 dose date – 1
	Week 16 (Month 4)	Week 12 dose date	Week 16 dose date – 1
	Week 20 (Month 5)	Week 16 dose date	Week 20 dose date – 1
	Week 24 (Month 6)	Week 20 dose date	Week 20 dose date + 27

^a Start Date (Day) = End date (day) of previous monthly interval + 1 if IP dose is not received

^b End Date (Day) = Start date (day) of current monthly interval + 27 if IP dose is not received

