5.4.3 Study Period

Baseline period is defined in **Table 3** and **Table 4** respectively. The efficacy and safety analyses will be summarized for the OLTP. The analysis window will be defined with the starting time point given by study day 1 after the 1st IP dose and end time point given by EOS date.

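### Read literally, the SAP's device-assignment rule starts baseline at the failed attempt for rescreened subjects who already had an eDiary, which conflicts with the 28-35 day baseline

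*SAP*

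**What the plan says.** SAP 5.4.1, Table 3, gives the baseline interval for all diary endpoints. It starts at "Device assignment date" and ends at "Day prior to study day 1". No maximum length is given. SAP 5.4.3 confirms that this table is the operative definition ("Baseline period is defined in" Table 3 for diary endpoints and Table 4 for the MFIQ). SAP 5.2 then defines the start date: "The date on which an eDiary device is assigned to a subject for the first time after completion of initial screening".

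The same SAP, in section 3.1, describes "A baseline period of 4 weeks (28 up to 35 days) to collect data on migraine headaches". Protocol 8.1.2 says the period "must be at least 28 days and no more than 35 days in duration".

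Protocol 8.1.2 also makes diary compliance below 75%, judged on day 1 after the baseline period, a reason for screen failure. It allows one rescreen and opens a new screening window, and it adds: "Subjects will retain the same subject identification number assigned at the original screening". The SAP has no rule for rescreened subjects.

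**The concern.** A subject who fails at the end of baseline has already been given an eDiary. Because the subject number does not change, the first assignment of a device to that subject belongs to the failed attempt, and nothing in the SAP resets it. Table 2 of the SAP prorates over all diary days in the interval. A literal derivation would therefore combine the failed baseline, any diary days between attempts, and the baseline that qualified the subject.

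Baseline MMD is the reference for the primary endpoint (at least a 50% reduction in mean MMD over months 4 to 6). It is also a covariate in the change-from-baseline and responder models in SAP Table 8, and in Appendix B where applicable. The same interval supplies baseline AMSMD, AHMD and pain severity. On this reading, part of the reference value comes from days that did not qualify the subject for enrolment.

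**Working it through.** **1. Interval length.** For a subject with one attempt, and a device assigned at the start of baseline, Table 3 gives the planned 28 to 35 days. For a subject who failed after a full first baseline, with no wait before rescreening:

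- shortest: 28 + 28 = 56 days
- longest: 35 (first baseline) + 21 (new screening window) + 35 (second baseline) = 91 days

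Any wait before rescreening adds to these figures.

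**2. Share of baseline taken from the failed attempt.** Under Table 2, MMD = 28 × migraine days / diary days. With d1 diary days in the failed attempt and d2 in the valid one, the failed attempt has weight d1/(d1 + d2). The diary counts below are illustrative. Under the 75% rule, 20 of 28 days (71%) and 26 of 35 days (74%) are both failures, and 21 of 28 just passes.

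| Failed attempt | Valid attempt | Weight of failed attempt |
|---|---|---|
| 20 of 28 | 28 of 28 | 20/48 = 42% |
| 20 of 28 | 21 of 28 | 20/41 = 49% |
| 26 of 35 | 21 of 28 | 26/47 = 55% |
| 35 of 35 (failed for another reason) | 21 of 28 | 35/56 = 62.5% |

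**3. Effect on one subject (assumed values).**

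- Lower frequency in the failed attempt: 6 migraine days on 20 diary days, then 12 on 28. The valid period alone gives 12/28 × 28 = 12.0. Pooled, (6 + 12)/(20 + 28) × 28 = 10.5. The 50% cut-off moves from 6.0 to 5.25, so a subject averaging 5.5 MMD changes from responder to non-responder.
- Higher frequency in the failed attempt: rates of 12 and then 8 MMD on the same diary days. Pooled, (20 × 12 + 28 × 8)/48 = 9.67. The cut-off moves from 4.0 to 4.83, so a subject averaging 4.5 MMD changes from non-responder to responder.

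**4. Effect across affected subjects (assumed values).** A simulation took mean MMD of about 10, a between-month SD of 0, 1.5 or 3, a response rate near 50%, 14, 20 or 28 diary days in the failed attempt, and 28 in the valid one. Between 6.9% and 12.2% of affected subjects changed responder status. The response rate among them moved by at most about 1 percentage point (largest change 52.1% to 51.0%).

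**5. Effect on the trial.** The plan's effective sample size reproduces: 1400 × 0.90 = 1260. The number rescreened after receiving a device is not given. If it were 1%, 5% or 10% of 1260, that would be about 13, 63 or 126 subjects. Applying 7% to the low end and 12% to the high end gives about 1 to 15 reclassified subjects (13 × 0.07 = 0.9; 126 × 0.12 = 15.1), or roughly 0.1% to 1.2% of 1260.

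**The case against.** The best defence is that the definition can be read per attempt. Initial screening may mean the pre-baseline eligibility step of whichever attempt is under way, as distinct from the day 1 check. Protocol 8.1.2 uses initial in that sense for the eligibility criteria that must be met before baseline. The reference to a first assignment may be there only to separate the original device from a replacement. SAP 5.4.1 calls the intervals 4-week, SAP 3.1 states 28 to 35 days, and SAP 5.3 takes "the monthly interval assessed (for endpoints derived from daily eDiary collection) before the first dose of investigational product". A programmer who read all of this would have reason not to pool two attempts. This stands as a plausible intention. However, no section states it, and SAP 5.3 does not say which attempt counts.

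Second, failed-attempt diary days may never reach the analysis data. Protocol 5.4 lists a minimal set of screen-failure data that does not name the eDiary. SAP 8.2 leaves the details of data held outside the main database to documents not available here. The point stands as an unknown. The only exclusion of diary days by date in the SAP is for days after the end-of-study date.

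Third, a reader might infer that failed baselines are in fact pooled, or that the primary association result is distorted. The documents support neither. Pooling needs both the literal reading and the presence of the data. The reclassification in step 4 runs in both directions, and nothing in the documents links it to genotype.

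**Conclusion.** The point holds as a conflict within the SAP, and between the SAP and the protocol, over a stated derivation rule. Taken literally, SAP 5.2 and Table 3 give a rescreened subject who failed after a full baseline an interval of at least 56 days, where both documents allow at most 35. Whether this alters any data depends on two things the documents leave open: how the definition is programmed, and whether failed-attempt diary days are available. If both go the wrong way, the failed attempt supplies about 42% to 55% of baseline in the compliance-failure examples, and some affected subjects change responder status.

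Only subjects who received a device, failed, were rescreened and then enrolled are exposed. Those who failed before receiving a device are not. Their number is unknown, and on the assumed range the effect on the overall result is probably small. The point is still worth settling before database lock, because it concerns the reference value of the primary endpoint and costs almost nothing to close.

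**What to change.** In SAP 5.2 and Table 3:

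- start the baseline interval at the start date of the baseline period (the baseline visit) of the screening attempt that led to enrolment;
- state that diary days from any failed attempt are excluded;
- cap the interval at 35 days before study day 1.

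The last device assignment date should not serve as the anchor. A device replaced during a valid baseline would then remove the earlier valid diary days. If fewer than 14 remained, Table 2 would set baseline MMD to missing, and the subject would drop out of the observed-data primary analysis.

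The corrected rule does not need the earlier data. At 75% compliance a 28-day baseline yields at least 0.75 × 28 = 21 diary days, above the 14-day minimum. The cost is a short change to the SAP text and the matching derivation code, with no change to study conduct.

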5.3 Study Points of Reference

Baseline Assessment

Baseline assessment for the endpoint of the interest is defined as the last non-missing measurement taken or the monthly interval assessed (for endpoints derived from daily eDiary collection) before the first dose of investigational product. In cases where baseline measurements are taken on the same day as IP, it will be assumed that these measurements are taken prior to IP being administered.

Study Day 1

Study Day 1 is defined as the first IP dose date.

Study Day

Study Day is defined as the number of days from Study Day 1.

Before Study Day 1:

$$\text{Study Day} = (\text{Date of Interest} - \text{Date of Study Day 1})$$

On or after Study Day 1:

$$\text{Study Day} = (\text{Date of Interest} - \text{Date of Study Day 1}) + 1$$

Therefore, the study day prior to Study Day 1 is -1.

5.4 Study Time Intervals

5.4.1 Monthly Intervals for Efficacy Endpoints Derived From Daily Diary Collection

The (4-week) monthly intervals for efficacy endpoints derived from daily eDiary collection will be determined based on each subject's monthly IP dosing dates. When an IP is

missed, discontinued, or no longer required, a 28-day monthly interval will be used. Any eDiary data occurring after EOS date will not be included in the analysis.

Applicable efficacy endpoints utilizing the monthly intervals in **Table 3** include:

- Monthly migraine days (MMD)
- Monthly acute migraine-specific medication days
- Monthly acute headache medication days
- Monthly average migraine pain severity

Table 3. Monthly Intervals for Efficacy Endpoints Derived From Daily Data Collection

Study Period	Assessment Timepoint	Monthly Interval	
		Start Date (Day) ^a	End Date (Day) ^b
Baseline Period	Baseline	Device assignment date	Day prior to study day 1
Open-label Treatment Period	Week 4 (Month 1)	Study Day 1	Week 4 dose date – 1
	Week 8 (Month 2)	Week 4 dose date	Week 8 dose date – 1
	Week 12 (Month 3)	Week 8 dose date	Week 12 dose date – 1
	Week 16 (Month 4)	Week 12 dose date	Week 16 dose date – 1
	Week 20 (Month 5)	Week 16 dose date	Week 20 dose date – 1
	Week 24 (Month 6)	Week 20 dose date	Week 20 dose date + 27

^a Start Date (Day) = End date (day) of previous monthly interval + 1 if IP dose is not received

^b End Date (Day) = Start date (day) of current monthly interval + 27 if IP dose is not received

5.4.2 Analysis Visits for Endpoints Based on Monthly Collection

Since the actual visit for a subject may not exactly coincide with their targeted visit date, the actual visit date is mapped to the analysis visit as in **Table 4**. Any data occurred after EOS date will not be included in the analysis.

For by-visit summaries, if more than one visit with non-missing measurement (including the unscheduled visits, ie, CPEVENT = 'UNSCHED') fall within the same visit window, the following rules will be applied according to the order described below for selecting one visit per visit window for summary:

1. Scheduled visit will be used regardless of the distance from the target day. Unscheduled visit will only be used when there is no measurement from scheduled visit in the visit window.
2. The visit closest to the target day among the same type of visits (scheduled vs. unscheduled) will be considered for analysis.
3. If two assessment dates are equidistant from the target date, the latter visit will be considered for analysis.

Table 4. MFIQ Analysis Visit Windows

Study Period	Analysis Visit	Target Day	Visit Window (Study Day)
Baseline Period	Day 1 (Baseline)	1	Last measurement ≤ Day 1
Open-label Treatment Period	Week 24 (Month 6)	169	156 to 183

5.4.3 Study Period

Baseline period is defined in **Table 3** and **Table 4** respectively. The efficacy and safety analyses will be summarized for the OLTP. The analysis window will be defined with the starting time point given by study day 1 after the 1st IP dose and end time point given by EOS date.

5.5 Subject Disposition

Exposed to Investigational Product

Subjects are defined as exposed if they receive at least one dose of investigational product. Subjects will be defined as having received IP if the observed data indicates they have received IP (IP date is non-missing) on a specific date, even if the IP quantity field is missing (IPQTY = NULL).

Completing the Investigational Product

Subjects are defined as completing investigational product if they complete IP at week 20. It will be derived from the End of IP eCRF with “Completed” as the primary reason for ending IP.

Completing Study

Subjects are defined as completing study if they complete the entire 24 weeks of study evaluation. It will be derived from the End of Study eCRF with “Completed” as the primary reason for ending study.

On-study

Subjects are considered on-study if they are enrolled and have not yet completed their EOS visit.

Dose Switch

Per protocol, dose switch is permitted at the discretion of the investigator at week 12. However, subjects could switch dose before or after week 12 if needed (e.g., adverse event). We define dose switch as an indicator variable indicating is a subject's dosage changed from their baseline dose at any time during the study.

5.6 Arithmetic Calculations

Migraine Disease Duration

The number of years from the diagnosis date (DXDT) of migraine (migraine with aura or migraine without aura, whichever is earlier) to the date informed consent is signed.

Observed Portion	Missing Portion	Duration of Migraine (Years)
Year, Month, Day	NA	(Informed Consent Date – DXDT) / 365.25
Year, Month	Day	[Year(Informed Consent Date) – Year(DXDT)] + [Month(Informed Consent Date) – Month(DXDT)] / 12 ^a
Year	Month, Day	[Year(Informed Consent Date) – Year(DXDT)] ^a

^a If it equals 0, add 1/12 years (ie, 1 month) to avoid a disease duration of 0.

Age at Onset of Migraine

Age at onset of migraine is defined as Age – duration of migraine.

Duration of IP Exposure

If subject switches dose,

- Duration before the First Switch = Minimum (Last Initial Dose Date + 27, First Switch Dose Date – 1) – First Dose Date + 1
- Duration on or after the First Switch = Minimum (Last Dose Date + 27, EOS Date) – First Switch Dose Date + 1

Otherwise,

- Duration = Minimum (Last Dose Date + 27, EOS Date) – First Dose Date + 1

Change From Baseline

Post-baseline monthly value – Baseline, as defined in Section [5.4](#).

If the baseline or post-baseline value is missing, the change from baseline value will be set to missing.

Percent Change From Baseline

The change from baseline divided by baseline and multiplied by 100:

$$(\text{Post-baseline} - \text{Baseline}) * 100 / \text{Baseline}$$

If the baseline value is 0 and the post-baseline value is also 0, the percent change from baseline is set to 0. If the baseline value is 0 and the post-baseline value is non-zero, then the percent change from baseline is set to missing.

Mean Monthly Change From Baseline Over Multiple Months

Arithmetic Mean monthly change from baseline is the arithmetic mean of the observed monthly change from baseline values for the months with non-missing change from baseline values.

Subject Incidence

The subject incidence for a given event in a given period is defined as the number of subjects with at least one reported occurrence of the event divided by the number of subjects who enter that period (ie, number of at-risk subjects). For subjects with multiple occurrences of the same event, the event will only be counted once per subject.

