During the open-label treatment period, subjects will continue with their daily eDiary use and additionally complete the Migraine Functional Impact Questionnaire version 2.0 at required visits. Blood samples will be collected for biomarker research. Subjects who participate in the CGRP biomarker substudy will have **3** additional blood samples collected at weeks 4, 12, and 24.

For a full list of study procedures, including the timing of each procedure, please refer to Section [8.2](#) and the Schedule of Activities in Section [1.3](#).

Statistical Considerations

The primary analysis will occur after all subjects have completed their week 24 or end of study visit.

[figure not shown]
For the primary endpoint, a genome-wide association study (GWAS) of Icelandic and Danish data will be performed using logistic regression for binary phenotypes. Assuming an additive model, GWAS will be performed for the overall sample and by pre-specified subgroups, in addition to other phenotypes of interest that may be defined from the study data. Age and sex will be used as covariates in Icelandic associations and age, sex, and 10 principal components will be used as covariates (to account for population structure) in Danish data. We use linkage disequilibrium (LD)-score regression to account for inflation in test statistics due to cryptic relatedness and stratification. A likelihood-ratio test will be used to compute all P-values. The Icelandic and Danish GWAS will be meta-analyzed using a fixed effects model. Weighted Bonferroni adjustment will be used to maintain a family-wise error rate of 0.05 (2-sided) for the primary endpoint. Using summary statistics from these studies (excluding GWAS data from Denmark and Iceland), mPRS will be calculated for the individuals participating in the clinical trial by summing their identified risk alleles, weighted by effect sizes and accounting for linkage disequilibrium using the LDpred software package. This genetic marker analysis will include subjects with non-missing clinical responses (responder [yes/no] based on at least a 50% reduction from baseline in mean MMD over months 4, 5, and 6).

For a full description of statistical analysis methods, please refer to Section 9.

Sponsor Name: Amgen, Inc

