5.1 Inclusion Criteria

Subjects are eligible to be included in the study only if all of the following criteria apply:

Before baseline period

- 101 Subject has provided informed consent prior to initiation of any study-specific activities/procedures.
- 102 Age \geq 18 years upon entry into screening
- 103 History of migraine (with or without aura) for \geq 12 months before screening according to the International Headache Society (IHS) Classification ICHD-3 (Headache Classification Committee of the International Headache Society, 2018) based on medical records and/or patient self-report
- 104 \geq 4 headache days that meet criteria as migraine days per month on average across the 3 months before screening

After baseline period

- 105 Must have demonstrated \geq 75% compliance in eDiary usage during baseline period

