≥ 14 diary days	Prorate to 28-day equivalent without rounding $\frac{\text{Number of frequency days within each monthly interval}}{\text{Number of diary days within each monthly interval}} \times 28$
< 14 diary days	Set to missing

Monthly Average Peak Migraine Pain Intensity

Peak pain intensity will be collected for **days with migraine headache reported**.

Monthly average **peak** migraine pain intensity is defined as the sum of the **reported peak** pain intensity **scores** during a monthly interval as defined in [Table 3](#) divided by the total number of **reported peak pain intensity scores**. If there is no migraine headache observed during the monthly interval, then the monthly average **peak** migraine pain intensity will be set to 0. If less than 14 days of eDiary data in each monthly interval are recorded, then the monthly average **peak** migraine pain intensity will be set to missing.

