6.3 Study-specific Analysis Sets

6.3.1 Observed Data Analysis Set

The observed data analysis set consists of a subset of subjects in FAS who receive at least 1 dose of investigational product and have an observed value for the endpoint of interest and pass the quality control procedures of genetic analysis. Primary analysis of

the efficacy endpoints related to the genetic biomarkers will utilize the observed data analysis set. Details of this analysis set is mentioned in the analysis plan developed by deCODE.

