Analysis of primary and exploratory objectives will be performed by deCODE. Amgen will provide the subject level clinical endpoints and covariates of interest to be analysed in relation to mPRS, sequence variants, and proteins. The analysis set for all deCODE performed analyses consists of individuals who receive at least one dose of investigational product, have an observed value for the endpoint of interest, pass all quality control procedures, and who are determined to be of Icelandic or Danish ancestry based on admixture analysis. Age, sex, dose switch (yes/no), and the baseline value of the clinical endpoint of interest (when applicable) will be used as covariates in all analyses. Additionally, principal components will be included as covariates in all Denmark related genomic analyses to account for population structure. Analyses will be run both with and without the dose switch (yes/no) and baseline clinical value

covariates to assess model robustness. All described analyses will be run separately in the Iceland and Denmark samples, and subsequently combined in a meta-analysis.

Genomic analyses will focus on a subset of 136 migraine variants found to be associated with migraine in previous literature instead of genome-wide analyses (9, 23). The rationale for focusing on this subset of migraine variants is to substantially reduce the multiple testing burden, since a Bonferroni genome-wide significance threshold = 5E-8 and a Bonferroni corrected threshold for the migraine variant subset = 0.05/136 = 3.7E-4.

Primary objective

To explore the relationship between clinical response to erenumab and genetic/proteomic biomarkers

Endpoint:

Achievement of at least a 50% reduction from baseline in mean monthly migraine days (MMD) over months 4, 5, and 6 in relation to each individual genome-wide significant single-nucleotide polymorphism (SNP) contributing to the migraine polygenic risk score (mPRS).

Method:

Test for association using logistic regression between migraine variants and the mPRS and whether individuals treated with erenumab achieve 50% reduction from baseline in MMD over months 4, 5, and 6. Individuals who do not achieve at least a 50% reduction are considered controls and those who achieve a least a 50% reduction are considered cases.

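### Subjects with no migraine days in the baseline diary get an outcome-dependent percent change (0 if still migraine-free, missing otherwise), and an interval without headache is given a pain score of 0 on a 1-to-10 scale

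*SAP*

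**What the plan says.** **Entry.** Protocol 5.1, criterion 104, requires at least 4 "headache days that meet criteria as migraine days per month on average across the 3 months before screening". That is history, taken before the diary starts. The one inclusion criterion placed after the baseline period, 105, asks for at least 75% "compliance in eDiary usage during baseline period". Neither 5.1 nor 5.2 sets a minimum for migraine days recorded in the baseline diary.

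**Percent change.** SAP 5.6 provides for a zero baseline in two ways. For a subject who stays at zero it says: "If the baseline value is 0 and the post-baseline value is also 0, the percent change from baseline is set to 0". A subject who starts at zero and later has any migraine days gets no percent change at all; the value is missing.

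**Who is analysed, and as what.** SAP Appendix B, under the primary objective: "Individuals who do not achieve at least a 50% reduction are considered controls". The observed data analysis set (SAP 6.3.1) is limited to treated subjects who "have an observed value for the endpoint of interest and pass the quality control procedures of genetic analysis". The Protocol synopsis agrees: "This genetic marker analysis will include subjects with non-missing clinical responses".

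**Pain intensity.** SAP 5.1.1 defines peak pain on a numerical scale from 1 to 10. Its rule for the monthly average has a special case, which opens: "If there is no migraine headache observed during the monthly interval". In that case the average is put at 0.

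**The concern.** A percentage reduction from a baseline of 0 is undefined. A workable rule treats all such subjects alike. The rule in SAP 5.6 separates them by what happens later: those who stay migraine-free get a usable value (0%), and those who have any migraine get none. If the responder flags are built on that value, the subjects with the better outcome remain and count as controls, while the others leave the analysis. The handling is asymmetric and penalises the better outcome. The flag is the phenotype for every SNP test, for the mPRS test of response and for the descriptive 50% and 75% rates. In the by-month versions of those rates, the same subject could enter and leave the denominator from month to month.

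The pain rule raises a separate problem. A month without migraine headache has no pain to score, yet it receives a value below the lowest point of the scale. At baseline that value enters the exploratory regressions of migraine severity on CGRP (SAP Table 8) and on mPRS (Appendix B, exploratory objective 3), since the SAP defines no other severity measure.

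**Working it through.** **1. The plan's own figure.** Effective sample size = 1400 × (1 − 0.10) = 1260, as SAP 3.2 states. The plan gives no figure for zero-baseline subjects.

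**2. What each possible derivation does.** Three derivations of the 50% flag are compatible with the text:

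| Derivation | Baseline 0, later 0 | Baseline 0, later above 0 |
|---|---|---|
| SAP 5.6 percent change ≤ −50 | control (0%) | missing, excluded |
| later value ≤ 0.5 × baseline | responder (0 ≤ 0) | control |
| Appendix B wording alone (no reduction achieved) | control | control |

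For a baseline above 0 the first two agree: from 8, later values of 0 and 4 are responders, and 8 and 12 are controls. For a baseline of 0 they disagree in every case. Because the endpoint is a mean over months 4 to 6, a single migraine day in any observed month moves a subject from the left column to the right.

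**3. How many subjects.** The documents give no diary distribution, so everything here is assumed: individual 28-day rates follow a gamma distribution truncated to 4 to 28, with mean about 8 to 11. The chance of zero days at rate m is e^(−m) under Poisson and 0.5^m under a negative binomial with variance 2m. Averaging over the rates and multiplying by 1400:

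- Poisson: about 2 to 4 subjects.
- Variance twice the mean: about 10 to 20.
- A variant with pre-truncation SD of 4 to 6 gives 1 to 3 and 6 to 15, the same order.
- Diary rates 40% below recalled history (0.6 × m), Poisson: about 10 to 33.
- Both together: about 35 to 90. Counts of 50 or more need both assumptions.

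As an extreme, if everyone sat at the entry threshold of 4, Poisson gives e^(−4) = 1.8%, or 23 of 1260. At 8 it gives 0.03%, or 0.4 subjects.

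**4. Effect on the response rate.** Suppose 1% of 1260 (12.6) have a zero baseline, half of them (6.3) stay at zero, and the other 1247.4 respond at the planned 50%, giving 623.7 responders.

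- Percent-change rule: 623.7 / (1247.4 + 6.3) = 49.75%.
- All zero-baseline subjects excluded: 623.7 / 1247.4 = 50.0%.
- Later value ≤ 0.5 × baseline: (623.7 + 6.3) / 1260 = 50.0%.

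At 5% with a zero baseline, the percent-change rule gives 48.7% against 50.0% with all excluded.

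**5. Effect on power.** Approximate power per SNP = Φ(√[n·p(1−p)·2·MAF(1−MAF)]·ln OR − z), with p = 0.5, MAF 0.1, OR 1.8 and two-sided alpha 0.05/136. The percent-change rule against excluding all gives 80.3% against 80.0% at 1% with a zero baseline, and 79.1% against 77.4% at 5%. The formula reflects only the number of subjects, not dilution from misclassification.

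**6. Effect on severity.** Assume true mean 6 and SD 1.5, with a fraction f set to 0. Variance ratio = [(1−f)·2.25 + f(1−f)·36] / 2.25 = (1−f) + 16f(1−f).

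- f = 0.2% (2.8 of 1400, the Poisson case): 0.998 + 0.032 = 1.03, about 3% more.
- f = 1% (14 of 1400, the overdispersed case): 0.990 + 0.158 = 1.15, about 15% more.

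**The case against.** The strongest objection is that the link to the primary endpoint is inferred. No sentence says the responder flag comes from percent change. SAP 5.6 also defines a mean absolute change over several months, and a flag built from that would make the zero-to-zero subject a responder and drop nobody. This stands, and the point is therefore conditional. It does not remove the need to act: the 50% and 75% endpoints are the only listed ones that need a relative change, the candidate derivations disagree for zero-baseline subjects, and the sponsor derives endpoints that deCODE then analyses.

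A reader might infer that the endpoint is scored backwards. The documents do not support that. A subject who goes from zero to zero has had no reduction, so control is literally correct, and a subject who worsens is dropped, not counted as a responder.

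A reader might also infer that nobody looks at baseline migraine counts. Protocol 8.2.2.1.1 has the investigator review the diary data at day 1 and confirm the relevant criteria. That review has no numeric minimum to apply, so a zero baseline can still pass. The baseline may also run to 35 days (Protocol 8.1.2), which makes zeros rarer.

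On severity, the endpoints are exploratory, SAP 8.5 plans histograms for outliers, and Table 8 adds a Spearman correlation with CGRP, which limits the influence of extreme values there. But a zero assigned by rule would count as valid and stay in the linear models, and Appendix B plans no rank-based check for severity against mPRS.

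**Conclusion.** The point holds as two narrow defects. First, the SAP leaves the responder derivation for a zero baseline unstated, and its only relative-change rule makes inclusion depend on the outcome if the flags use it. Second, the pain rule assigns an off-scale value; that does not depend on how the responder flag is derived.

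The size is probably small: a few to about 20 of 1400, and only those who also stay at zero through months 4 to 6 would become controls. A reader might conclude that the SNP results are at risk. The figures do not show that: with 1% zero baselines the response rate moves by a quarter of a percentage point and approximate power by 0.3 points. The severity regressions are more exposed, with about 3% to 15% extra variance over the same range of counts. All counts rest on the assumed distribution of migraine days, and the variance figures also on an assumed mean of 6 and SD of 1.5.

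**What to change.** 1. In SAP 5.6, write out how the 50% and 75% responder flags are derived. Set percent change and both flags to missing for every subject with baseline MMD of 0, whatever the post-baseline value, and report how many there are.
2. In SAP 5.1.1, set monthly average peak pain intensity to missing, not 0, when no peak pain score was reported in the interval.

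The cost is two short edits and a few fewer subjects in the responder and severity analyses. An additional primary run limited to subjects with at least 4 diary migraine days at baseline is not needed for this point: it would remove validly enrolled subjects by a diary threshold that the protocol does not set.
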